8.2 Other Efficacy Analyses

Descriptive statistics of the actual value, change from baseline, and percent change from baseline will be calculated at each time point for HDL-C, TG, and LDL-C (Friedewald formula).

8.3 Subgroup Analyses

Subgroup analyses will be performed by the following items for the percent change in LDL-C (direct method) from baseline at Weeks 24 and 52. Statin intensity categories and types are shown in [Appendix 6](#). In the data for each statin type, subjects who use multiple medications will be excluded from the summarization.

- Statin response (inadequate response to statins/difficulties in treatment with statins)
- Sex (Male, Female)
- Familial hypercholesterolemia (Yes, No)
- Diabetes mellitus (Yes, No)
- Age (<65 years, ≥65 years and <75 years, ≥75 years)
- Statin use (Yes, No)
- BMI (<25 kg/m², ≥25 kg/m² and <30 kg/m², ≥30 kg/m²)
- eGFR (<60 mL/min/1.73 m², ≥60 mL/min/1.73 m² and <90 mL/min/1.73 m², ≥90 mL/min/1.73 m²)
- LDL-C at baseline (<100 mg/dL, ≥100 mg/dL and <120 mg/dL, ≥120 mg/dL and <140 mg/dL, ≥140 mg/dL)
- Statin intensity (Low-intensity statins, High-intensity statins, No statins)
- Statin type (atorvastatin calcium trihydrate, fluvastatin sodium, pitavastatin calcium, pravastatin sodium, rosuvastatin calcium, simvastatin, no statins)

9 Safety Analyses

For the safety analysis set, the summarization will be performed by rollover, newly enrolled, and overall subjects. Baseline is defined as the last data before the start of IMP administration. The analysis visits will be Weeks 4, 8, 12, 16, 20, 24, 28, 32, 36, 40, 44, 48, and 52, unless otherwise specified. The same analysis will be performed for each statin response (inadequate response to statins/difficulties in treatment with statins). Summarization at the Last Visit will also be performed in addition to summarization at each time point.

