## 1.2 Schema

Screening Period (2 weeks)	Treatment Period (52 weeks, Open-label)	Follow-up Period (4 weeks)
-------------------------------	--	-------------------------------

[Rollover subjects from Trial 346-102-00002 will proceed directly to the treatment period of this trial (52 weeks, open-label) after completing the 12-week double-blind treatment period.]

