**Figure 1.2-1 Trial Design Schematic**

### 1.3 Schedule of Assessments

	Screening Period		Treatment Period														Follow-up Period (28 days after the final IMP administration)
	Rollover Subjects	Newly Enrolled Subjects															
Visit (Week)	-4 a	-2	0 b	4	8	12	16	20	24	28	32	36	40	44	48	52/ Discontinuation c	56
Trial Day	-28 ± 3	-14 ± 7	1	29 ± 7	57 ± 7	85 ± 7	113 ± 7	141 ± 7	169 ± 7	197 ± 7	225 ± 7	253 ± 7	281 ± 7	309 ± 7	337 ± 7	365 ± 7	393 ± 7
Informed consent d	●	●															
Eligibility assessment	●	●	●														
Demographics		●															
Physical examination	●	●	●	●	●	●	●	●	●	●	●	●	●	●	●	●	●
Body weight		●	●	●		●		●	●	●		●		●		●	●
Endocrine test (TSH), virus test (HBsAg, HCV antibody)		●															
Vital signs e	●	●	●	●	●	●	●	●	●	●	●	●	●	●	●	●	●
12-Lead ECG f		●	●			●			●			●				●	
Clinical laboratory tests g	●	●	●	●	●	●	●	●	●	●	●	●	●	●	●	●	●
Fasting lipids h, i	●	●	●	●	●	●	●	●	●	●	●	●	●	●	●	●	
HbA1c i		●	●			●			●			●				●	
hsCRP, apo B l			●			●			●			●				●	
Confirmation of use of concomitant medications/therapies	←																→
Adverse events	←																→
Pregnancy test j		●	●			●			●			●				●	
Blood sampling for DNA storage k			○														
Dispensing of IMP			●	●	●	●	●	●	●	●	●	●	●	●	●		
Provision of subject diary			●	●	●	●	●	●	●	●	●	●	●	●	●		
Collection of unused IMP and subject diary				●	●	●	●	●	●	●	●	●	●	●	●	●	

● Mandatory; ○ Optional

- aThe results of the scheduled tests performed at Week 8 in the phase 3 confirmatory trial (Protocol No. 346-102-00002) will be used.
- bBody weight and 12-lead ECG will not be required on Day 1 if they have been performed within 7 days prior to Day 1 in the screening period. The results of the scheduled tests performed at Week 12 in the phase 3 confirmatory trial (Protocol No. 346-102-00002) will be used for rollover subjects.
- cIn cases of early discontinuation during the treatment period, the same assessments as in Week 52 are to be performed at Discontinuation Visit within 2 days after the last dose of the IMP as far as possible.

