- dWritten informed consent will be obtained from the patient himself/herself prior to any trial-related assessments. Written informed consent will be obtained by Week -2 for newly enrolled subjects, and by Week 12, but on or after Week 8 in the phase 3 confirmatory trial (Protocol No. 346-102-00002) for rollover subjects (before the start of Day 1 of this trial).
- eBody temperature, blood pressure, and pulse rate measurements are to be performed after resting for at least 5 minutes. Vital signs should be measured before blood collection whenever possible to minimize effects on the assessment.
- f12-Lead ECG is to be performed after resting for at least 10 minutes. The 12-lead ECG should be performed before blood collection whenever possible to minimize effects on the assessment.
- gClinical laboratory tests include hematology, blood chemistry (except for HbA1c, fasting lipid assessments), and urinalysis.
- hFasting lipid assessments include LDL-C, HDL-C, non-HDL-C, TC, and TG.
- iOn scheduled visit days, subjects are to be instructed to come to the trial site without taking the IMP and reminded to take the IMP after tests are completed.
- jPregnancy test is to be performed only for females of childbearing potential. If urine test is positive, the serum test will be performed (except Week -2).
- kBlood sampling for DNA storage will only be performed for subjects who provide written consent for sample collection. Blood sampling for DNA storage will be performed before IMP administration on Day 1 in principle. If blood sampling cannot be performed or needs to be performed again, it will be performed at a feasible time during the trial period.

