### **9.4 Statistical Analyses**

#### **9.4.1 Efficacy Analyses**

Efficacy analyses will be performed using the efficacy analysis set by rollover subjects, newly enrolled subjects, and overall (rollover and newly enrolled) subjects. Baseline is defined as the last data before the start of IMP administration in the treatment period.

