3.4 Trial Visit Window

For the efficacy and safety endpoints (except for AEs), acceptable windows of analysis visits will be set, and the analysis will be based on the analysis visits, regardless of the time points recorded in the case report form (CRF). Analysis visits will be specified based solely on fasting data for non-HDL-C, TC, HDL-C, TG, and LDL-C (calculated using the Friedewald formula) among the fasting lipid parameters for the efficacy endpoints. The handling of fasting data is described in [Section 5.3](#).

Acceptable windows of analysis visits are shown in [Table 3.4-1](#). The start day of investigational medicinal product (IMP) administration is defined as Day 1. Baseline is defined as the last data before the start of IMP administration. If multiple data points are available for a certain acceptable window, the last data point will be used for the analysis. Data collected more than 2 days after the last IMP administration will be excluded. The last data obtained between the initial IMP administration and 2 days after the last IMP administration will be defined as the Last Visit.

Table 3.4-1 Acceptable Windows of Analysis Visits	
Week	Trial Day Interval
Baseline	- 1
Week 4	2 - 43
Week 8	44 - 71
Week 12	72 - 99
Week 16	100 - 127
Week 20	128 - 155
Week 24	156 - 183
Week 28	184 - 211
Week 32	212 - 239
Week 36	240 - 267
Week 40	268 - 295
Week 44	296 - 323
Week 48	324 - 351
Week 52	352 - 375
Last Visit	Last data obtained between the initial IMP administration and 2 days after the last IMP administration in the treatment period
Week 56 (FU)	Time point recorded in the CRF

4 Sample Size

Assuming a withdrawal of approximately 20 subjects during the treatment period, the target number of subjects is set at 120 to ensure that 100 subjects will complete the 1-year treatment to assess the safety of ETC-1002 at 180 mg in long-term administration.

5 Statistical Analysis Datasets

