- CT-5.2-1 Efficacy Analysis: Descriptive Statistics for Values, Change and Percent Change From Baseline in Efficacy Parameters (Efficacy Analysis Set)
- CT-5.2-2 Efficacy Analysis: Descriptive Statistics for Values, Change and Percent Change From Baseline in Efficacy Parameters by Statin Response (Efficacy Analysis Set)
- CT-5.3-1 Efficacy Analysis: Incidence of Subjects who Achieved the Target Value in LDL-C (Efficacy Analysis Set)
- CT-5.3-2 Efficacy Analysis: Incidence of Subjects who Achieved the Target Value in LDL-C by Statin Response (Efficacy Analysis Set)
- CT-5.4-1 Other Efficacy Analysis: Descriptive Statistics for Values, Change and Percent Change From Baseline in Efficacy Parameters (Efficacy Analysis Set)
- CT-5.4-2 Other Efficacy Analysis: Descriptive Statistics for Values, Change and Percent Change From Baseline in Efficacy Parameters by Statin Response (Efficacy Analysis Set)

CT-5.5	Subgroup Analysis: Percent Change From Baseline in LDL-C by Statin Response (Efficacy Analysis Set)
CT-5.6	Subgroup Analysis: Percent Change From Baseline in LDL-C by Sex (Efficacy Analysis Set)
CT-5.7	Subgroup Analysis: Percent Change From Baseline in LDL-C by Familial Hypercholesterolemia (Efficacy Analysis Set)
CT-5.8	Subgroup Analysis: Percent Change From Baseline in LDL-C by Diabetes Mellitus (Efficacy Analysis Set)
CT-5.9	Subgroup Analysis: Percent Change From Baseline in LDL-C by Age (Efficacy Analysis Set)
CT-5.10	Subgroup Analysis: Percent Change From Baseline in LDL-C by Statin Therapy (Efficacy Analysis Set)
CT-5.11	Subgroup Analysis: Percent Change From Baseline in LDL-C by BMI (Efficacy Analysis Set)
CT-5.12	Subgroup Analysis: Percent Change From Baseline in LDL-C by eGFR (Efficacy Analysis Set)
CT-5.13	Subgroup Analysis: Percent Change From Baseline in LDL-C by Baseline LDL-C (Efficacy Analysis Set)
CT-5.14	Subgroup Analysis: Percent Change From Baseline in LDL-C by Baseline Statin Intensity (Efficacy Analysis Set)
CT-5.15	Subgroup Analysis: Percent Change From Baseline in LDL-C by Baseline Statin Medication (Efficacy Analysis Set)
CT-7.1-1	Extent of Exposure to Investigational Medicinal Product (Safety Analysis Set)
CT-7.1-2	Extent of Exposure to Investigational Medicinal Product by Statin Response (Safety Analysis Set)
CT-7.2-1	Treatment Compliance (Efficacy Analysis Set)
CT-7.2-2	Treatment Compliance by Statin Response (Efficacy Analysis Set)
CT-7.3-1	Treatment Compliance (Safety Analysis Set)

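### The baseline LDL-C subgroup table groups newly enrolled subjects by the same single pre-dose value that is the denominator of their percent change, so it shows a gradient even if the drug works equally in everyone

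*SAP*

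**What the plan says.** SAP 8.3 plans subgroup summaries of the "percent change in LDL-C (direct method) from baseline at Weeks 24 and 52". One of the eleven subgroup factors is "LDL-C at baseline (<100 mg/dL, ≥100 mg/dL and <120 mg/dL, ≥120 mg/dL and <140 mg/dL, ≥140 mg/dL"). Appendix 8 lists the output as CT-5.13, "Subgroup Analysis: Percent Change From Baseline in LDL-C by Baseline LDL-C (Efficacy Analysis Set").

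SAP 3.4 states: "Baseline is defined as the last data before the start of IMP administration". Protocol 9.4.1 agrees. Nothing is averaged with an earlier value, and no adjustment or caution on interpretation is planned for this table.

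An earlier LDL-C exists. Table 1.3-1 of the protocol schedules fasting lipids at Week -2 in newly enrolled subjects as well as on Day 1, and footnote h says "Fasting lipid assessments include LDL-C, HDL-C, non-HDL-C, TC, and TG". Inclusion criterion 4 (Protocol 5.2.1) requires a screening LDL-C of at least 100, 120 or 140 mg/dL, depending on risk category.

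For rollover subjects, the Day 1 column is filled from the earlier trial: "The results of the scheduled tests performed at Week 12 in the phase 3 confirmatory trial" (Table 1.3-1, footnote b). Their Week -4 column uses that trial's Week 8 results (footnote a). They enter "after completing the 12-week double-blind treatment period" (Protocol 1.2).

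SAP section 8 already reports every efficacy analysis for rollover, newly enrolled and overall subjects. SAP 7.3 tabulates baseline LDL-C with the same four cut-points.

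**The concern.** A subject whose pre-dose value is high by chance is placed in a higher row and given a larger denominator. The next value tends to be lower, and the percent change looks like a better response. A value low by chance does the opposite. The entry rule sharpens this at the low end: a newly enrolled subject below their own entry cut-off at baseline is there because the later reading was lower than the screening reading.

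In a controlled trial the same pattern would appear in the control arm and could be subtracted. Here it cannot be. The cut-points 100, 120 and 140 mg/dL are also the trial's own lipid management goals, so a reader is likely to take the rows as showing which patients benefit more.

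**Working it through.** The plan gives no figure for a baseline gradient, so there is none to reproduce. Its sample size sum (100 completers + 20 withdrawals = 120) plays no part here.

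**Structure.** Let T be a subject's usual LDL-C, with independent multiplicative errors e_B at baseline and e_F at follow-up, and the same drug effect in everyone.

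- Baseline B = T × e_B
- Follow-up F = T × 0.7874 × e_F, where 0.7874 = 1 - 0.2126
- Percent change = 100 × (F/B - 1) = 100 × (0.7874 × e_F/e_B - 1)

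T cancels, so the percent change does not depend on the subject's usual level. It does depend on e_B, and grouping on B selects on e_B. With zero within-subject variation the gradient is exactly zero; with any variation it is not.

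**Inputs from the documents.** Effect -21.26% at 180 mg, Week 12 of the phase 2 trial (Protocol 2.1); entry cut-offs (Protocol 5.2.1); row cut-points (SAP 8.3).

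**Assumed, not in the documents.** Median LDL-C 130 mg/dL before selection, log SD 0.18, a single entry cut-off of 120 mg/dL, within-subject CV of 5, 7 or 10%, and errors independent between visits.

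**Newly enrolled subjects, grouped by the pre-dose value** (simulated mean percent change):

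| CV | Drug effect | 100 to <120 | 120 to <140 | ≥140 | Gap, outer rows |
|---|---|---|---|---|---|
| 5% | none | +5.0 | +1.1 | -1.2 | 6.2 |
| 5% | -21.26% | -17.3 | -20.4 | -22.2 | 4.9 |
| 7% | none | +7.2 | +2.0 | -2.1 | 9.3 |
| 7% | -21.26% | -15.6 | -19.7 | -22.9 | 7.3 |
| 10% | none | +10.3 | +3.5 | -3.6 | 13.9 |
| 10% | -21.26% | -13.2 | -18.5 | -24.1 | 10.9 |

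The rows with drug effect follow from the others by multiplication. At CV 7%, for example, 1.072 × 0.7874 = 0.844, which is -15.6%.

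**Grouped by the screening value, CV 10%, same effect.** The result is -20.5% in both occupied rows. The small shift from -21.26% is common to all rows: the ratio of two noisy values averages 1 + CV², and 0.7874 × 1.01 = 0.795. The gradient is gone.

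**Wider assumptions.** These use three entry cut-offs with an assumed 30/50/20% risk mix, mean LDL-C 145 mg/dL before selection, between-subject SD 20 to 40 mg/dL and CV 5 to 15%. The gap between ≥140 and 100 to <120 is about 2 to 20 points, always in the same direction. The <100 row holds about 0.1 to 4% of newly enrolled subjects. Grouping by the mean of screening and pre-dose values only shrinks the gradient (SD 30, CV 10%: slope -0.73 instead of -1.21 points per 10 mg/dL).

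**Rollover subjects.** Allocation in the confirmatory trial is not given. Assume half were on active drug, entry to that trial used the same 120 mg/dL cut-off, CV 7% and the same effect. For <100 / 100 to <120 / 120 to <140 / ≥140:

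- by the pre-dose value: +5.4 / -2.7 / -13.0 / -20.5
- by the Week 8 value: +0.3 / -3.6 / -12.6 / -18.1

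Subjects already on drug are low at both visits and have little further to fall. With rollovers assumed to be 25% of all subjects, grouping everyone by the earlier value widens the overall gap between ≥140 and 100 to <120 from 22.5 - 9.6 = 12.9 to 20.4 - 3.6 = 16.8 points, because the low rows then hold only rollovers.

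**The case against.** The table is one of eleven descriptive subgroup summaries in a safety trial. SAP section 6 declares no primary or secondary outcome variables, no interaction test is planned, and nothing in the plan states who benefits. That is correct and limits the weight of the point. A reader might infer that the plan makes a false claim of effect modification; it does not. The risk is in how the rows will be read.

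A reader might take the no-drug spread of 9 to 14 points (CV 7 to 10%) as the size of the error. With the phase 2 effect acting proportionally, the same model gives about 7 to 11 points. Every variance input is assumed, so even that is not a prediction.

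A reader might infer that the gradient cannot be repaired once the trial is done. The documents do not support this: fasting lipid values for screened subjects are listed (SAP Appendix 9, LAB-2), so regrouping stays possible. Specifying it in advance only avoids a post hoc change.

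A reader might also suppose that an untreated earlier value exists for everyone. It does not: the rollovers' Week -4 value comes from double-blind treatment, so regrouping does not cure their rows.

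Finally, the separate display of newly enrolled subjects is already planned, and a change to SAP 8.3 alone would break agreement with the SAP 7.3 baseline tables. Both points stand and shape the fix.

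**Conclusion.** The point holds for newly enrolled subjects. Using one pre-dose value as both grouping variable and denominator, without a control arm, produces a gradient in favour of higher LDL-C when the true effect is constant. Its size is about 5 to 11 points between the ≥140 and 100 to <120 mg/dL rows at an assumed CV of 5 to 10% with a single 120 mg/dL cut-off, and about 2 to 20 points over the wider assumptions. Its direction needs only non-zero within-subject variation.

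A real gradient may also exist, and the planned table cannot separate the two. Grouping by the Week -2 value removes the artefact in so far as the errors at Week -2 and at baseline are independent. For rollover and overall rows, carry-over from the confirmatory trial gives a gradient under either grouping, so neither should be read for effect modification.

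This is an inexpensive improvement to one descriptive table. The primary safety objective and the overall LDL-C result are not affected.

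**What to change.** - In SAP 8.3 and CT-5.13, for newly enrolled subjects, form the LDL-C categories from the Week -2 screening LDL-C (direct method). Keep the pre-dose baseline as the denominator of the percent change.
- Name which screening value counts when a re-test was done, since Protocol 1.3.1.2 permits re-testing.
- Merge the lowest row, which will be empty or nearly so because of the entry rule.
- The planned table by baseline category may stay beside it for agreement with SAP 7.3, labelled as affected by regression to the mean.
- Do not apply the screening-based grouping to rollover subjects. Add a note that the rollover and overall rows are not to be read for effect modification, because their Week -4 and Day 1 values come from Weeks 8 and 12 of the double-blind trial.

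Cost: one derived variable from data already collected and a few lines of SAP text. The downsides are fewer newly enrolled subjects in the low categories and categories that differ from those in the baseline tables.

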9.1 Extent of Exposure

Descriptive statistics will be calculated for the duration of IMP treatment in the treatment period (Date of final IMP administration – Date of initial IMP administration + 1) and for the total number of days of IMP administration (total number of days taking the IMP in the treatment period). For the duration of IMP treatment, frequency distributions of categorized durations (days) (1-84, 85-168, 169-252, 253-336, and ≥ 337) will be calculated by rollover, newly enrolled, and overall subjects, along with the descriptive statistics.

9.2 Adverse Events

All AEs will be coded by system organ class (SOC) and preferred term (PT) using the Medical Dictionary for Regulatory Activities (MedDRA) version 26.1. The incidence of the following events will be calculated by SOC, PT, and overall. If a subject experiences the same event more than once, the more severe event will be used.

- Treatment-emergent AEs (TEAEs)
- TEAEs by severity
- TEAEs with an outcome of death
- Serious TEAEs
- TEAEs leading to discontinuations of the IMP

Treatment-emergent AEs that are potentially causally related to the IMP will be summarized in the same manner. Summary tables (only for events occurring in $\geq 5\%$ of all subjects) will be prepared for TEAEs and for TEAEs that are potentially causally related to the IMP.

The number of subjects with TEAEs and the incidence by PT will be shown by initial onset time (days) (1-14, 15-28, 29-56, 57-84, 85-168, 169-252, 253-336, ≥ 337 , after the end of treatment). Treatment-emergent AEs that are potentially causally related to the IMP will be summarized in the same manner.

The incidence of TEAEs that are not judged to be adverse reactions to the COVID-19 vaccine will be calculated by SOC, PT, and overall.

9.2.1 Adverse Events of Special Interest

The incidence of AEs of special interest will be calculated by SOC and PT.

Adverse events of special interest that are potentially causally related to the IMP will be summarized in the same manner. The classification of the AEs of special interest is shown in [Appendix 5](#).

9.2.2 Subgroup Analyses of Adverse Events

The number of subjects with TEAEs and the incidence will be calculated by SOC and PT for each of the following subgroups. Treatment-emergent AEs that are potentially causally related to the IMP will be summarized in the same manner. Statin intensity categories and types are shown in [Appendix 6](#). In the data for each statin type, subjects who use multiple medications will be excluded from the summarization.

- Sex (Male, Female)
- Familial hypercholesterolemia (Yes, No)
- Diabetes mellitus (Yes, No)
- Age (<65 years, ≥65 years and <75 years, ≥75 years)
- Statin use (Yes, No)
- BMI (<25 kg/m², ≥25 kg/m² and <30 kg/m², ≥30 kg/m²)
- eGFR (<60 mL/min/1.73 m², ≥60 mL/min/1.73 m² and <90 mL/min/1.73 m², ≥90 mL/min/1.73 m²)
- Statin intensity (Low-intensity statins, High-intensity statins, No statins)
- Statin type (atorvastatin calcium trihydrate, fluvastatin sodium, pitavastatin calcium, pravastatin sodium, rosuvastatin calcium, simvastatin, no statins)

For AEs of special interest, the number of subjects with the events and the incidence will be calculated by SOC and PT for each of the following subgroups. Adverse events of special interest that are potentially causally related to the IMP will be summarized in the same manner.

- eGFR (<60 mL/min/1.73 m², ≥60 mL/min/1.73 m² and <90 mL/min/1.73 m², ≥90 mL/min/1.73 m²)

9.3 Clinical Laboratory Data

Among the urinalysis parameters in laboratory tests, those other than pH and specific gravity will be included in the qualitative urinalysis.

For parameters other than the qualitative urinalysis, descriptive statistics of the actual value and change from baseline will be calculated at each time point. For qualitative urinalysis parameters, shift tables at each time point from baseline will be prepared. For parameters other than qualitative urinalysis, measured values will be categorized using

the reference range to “below the lower limit of reference range,” “within the reference range,” and “above the upper limit of reference range,” and shift tables at each time point from baseline will be prepared.

The number and percentage of subjects meeting the criteria for identifying laboratory values of potential clinical relevance ([Appendix 2: Criteria for Identifying Laboratory Values of Potential Clinical Relevance](#)) and Hy’s law ([Appendix 7: Criteria for Hy’s Law](#)) after IMP administration will be calculated. All data obtained after IMP administration during the treatment period will be analyzed, including those obtained at unscheduled visits.

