## 2.3 Known and Potential Risks and Benefits

In a drug-interaction trial conducted outside Japan, administration of ETC-1002 at 180 mg/day increased the exposure to simvastatin lactone approximately 1.2 to 1.3 fold and the exposure to simvastatin hydroxy acid approximately 2 fold. [REDACTED]

[REDACTED]

[REDACTED]

[REDACTED]

[REDACTED]

[REDACTED]

[REDACTED]

[REDACTED]

[REDACTED]

Serum uric acid increased was observed in the clinical trials conducted outside Japan. In pooled data from the phase 3 placebo-controlled trials, mean uric acid levels increased within the first 1 month, and then remained stable and returned to baseline in subjects who discontinued ETC-1002 for any reason. Serum uric acid increased may have been caused by inhibition of renal tubular organic anion transporter 2 by ETC-1002. Gout was reported in 1.4% of subjects receiving ETC-1002 and 0.4% of subjects receiving placebo. The slightly higher incidence of gout in the ETC-1002 group may be due to increased uric acid caused by ETC-1002.

Although gout did not occur in the Japanese phase 2 trial, blood uric acid increased was observed in 6 subjects (4.3%) and hyperuricaemia was observed in 5 subjects (3.5%) in the ETC-1002 groups. However, uric acid levels decreased rapidly after discontinuation in all subjects. Increased uric acid levels as an AE may cause gout, and is considered to be a significant potential risk.

The results of the clinical trials conducted outside Japan and the Japanese phase 2 trial have demonstrated that ETC-1002 at 180 mg/day was effective in patients with inadequate response to statins or statin intolerance. For safety, ETC-1002 was tolerated at up to 180 mg/day with no tendency for an increased incidence of AEs in a dose-dependent manner. In addition, the incidence of muscle-related AEs or AEs associated with hepatic impairment, which are considered to be risk factors affecting drug adherence, was not significantly different from those in the placebo group. In the long-term trials conducted outside Japan, no new safety signals were identified for the long-term administration of ETC-1002 with the efficacy continuing to the end of the trial.

ETC-1002 can be a useful treatment for patients with hyper-LDL cholesterolemia who need to continue long-term therapy for hyper-LDL cholesterolemia.

Once the IB is revised, the revised version will be provided to the trial sites. The trial sites should refer to the most current version provided as needed.

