## **4.2 Scientific Rationale for Trial Design**

This trial has been planned as an open-label trial with the primary objective of assessing the safety of ETC-1002 for 52 weeks in patients with hyper-LDL cholesterolemia based on “The Extent of Population Exposure to Assess Clinical Safety for Drugs Intended for Long-term Treatment of Non-Life-Threatening Conditions (PAB/ELD Notification No. 592 dated 24 May 1995).” The trial population will include patients with hyper-LDL cholesterolemia with inadequate response to statins or difficulty in treatment with statins who cannot achieve the lipid management goals specified in the Japan Atherosclerosis Society Guidelines for Prevention of Atherosclerotic Cardiovascular Diseases 2017, and who are expected to similarly respond to ETC-1002 based on the results observed in the previous trials conducted outside Japan and the Japanese phase 2 trial.

Warnings for hyperuricaemia and tendon rupture are provided in the non-Japanese package insert for ETC-1002. In the Japanese phase 2 trial, AEs related to hyperuricaemia (all events were moderate or lower in severity) also occurred in 7.8% (11/141 subjects) of the Japanese subjects treated with ETC-1002. Furthermore, the results of clinical trials conducted outside Japan have shown that the concomitant use of ETC-1002 with statins increases exposure to the statins. Based on the above, laboratory values such as uric acid and CK levels will be monitored regularly to minimize safety risks in the subjects during the trial. In addition, although tendon rupture did not occur in the Japanese phase 2 trial, it is considered necessary to continue to evaluate this AE in long-term administration as an AE of special interest in this trial.

Taken together, the trial design has been determined to be scientifically and ethically rational as the design can be feasibly implemented, while also ensuring the safety of the subjects.

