### **8.7.1 Clinical Laboratory Assessments**

Clinical laboratory samples will be collected at the time points described in the Schedule of Assessments (Table 1.3-1) to perform the clinical laboratory assessments described in [Section 10.2](#). The total volume of blood to be collected during the trial will be documented in the electronic informed consent form (eICF)/ICF.

On the day of the tests shown in the Schedule of Assessments (Table 1.3-1), subjects will be asked to visit the trial site in a fasting state (at least 10 hours of fasting [including abstaining from sugar-containing beverages such as juice]) without taking the IMP, and blood and urine samples will be collected from each subject. The date and time of blood sampling, date of urine sampling, and the fasting state at the time of blood sampling will be recorded in the source document and the eCRF. The sponsor will select a central laboratory for this trial. The test results measured by the central laboratory will be used to confirm the eligibility. Proper sample collection, handling, and shipping procedures will be provided to the trial sites in a separate manual prior to the start of the trial. The central laboratory will report the test results to the investigator or subinvestigator who confirms the results. The laboratory report will be officially documented by entering the date of confirmation and signing the report by the investigator or subinvestigator. The test results will be directly reported to the sponsor by the central laboratory in electronic files. Therefore, it is not necessary to record the results in the source document and the eCRF.

Since serum uric acid increased was observed with administration of ETC-1002 in the clinical trials conducted outside Japan, the US package insert includes a cautionary statement that the presence or absence of signs and symptoms of hyperuricemia at administration of ETC-1002 should be monitored and treatment with antihyperuricemics should be initiated as necessary. The investigator or subinvestigator will check the results of uric acid measurements in subjects on and after Day 1 and take appropriate measures as necessary. Since ETC-1002 exposure in blood was increased by administration of probenecid in the clinical trials conducted outside Japan, antihyperuricemics other than probenecid should be administered if drug therapy for uric acid increased is required for the subject.

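### Late-visit uric acid means and shift tables keep values measured after a urate-lowering drug is started, so the change under ETC-1002 is understated to the extent such drugs are used

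*SAP*

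**What the plan says.** **Analysis.** SAP 9.3 states: "For parameters other than the qualitative urinalysis, descriptive statistics of the actual value and change from baseline will be calculated at each time point". Uric acid is one of these parameters (Protocol Table 10.2-1). The same section plans shift tables against the reference range at each time point, and SAP 9 adds a Last Visit summary. SAP 3.4 drops values taken more than 2 days after the last dose of study drug. Neither that section nor SAP 5.3 on missing data mentions urate-lowering drugs.

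SAP Appendix 2 sets a uric acid criterion of 9 mg/dL or more, with no change-from-baseline condition. For the count of subjects meeting it, SAP 9.3 says: "All data obtained after IMP administration during the treatment period will be analyzed, including those obtained at unscheduled visits".

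**Conduct.** Under Protocol 8.7.1 the investigator "will check the results of uric acid measurements in subjects on and after Day 1 and take appropriate measures as necessary", and "antihyperuricemics other than probenecid should be administered if drug therapy for uric acid increased is required for the subject".

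**Importance.** Protocol 2.3 says: "Increased uric acid levels as an AE may cause gout, and is considered to be a significant potential risk". It also reports that in placebo-controlled trials outside Japan "mean uric acid levels increased within the first 1 month, and then remained stable". Protocol 4.2 says that "laboratory values such as uric acid and CK levels will be monitored regularly to minimize safety risks in the subjects during the trial".

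**The concern.** Whether a subject receives a urate-lowering drug depends on the measurement being summarised. The subjects with the highest uric acid are the likeliest to be treated, and from then on their values reflect ETC-1002 plus another drug. Those values enter the later means, shift tables and Last Visit summary unmarked, so any bias runs downward and can build up over the visits.

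The primary objective is safety over 52 weeks, and one thing this trial can show is whether the early rise persists in Japanese patients. That answer comes from the late visits, which are the affected ones. The trial is uncontrolled, so no comparator would expose the artefact. A mean that rises by Week 4 and then drifts down could be read as adaptation to ETC-1002 when part of the drift comes from added treatment. No table listed in SAP Appendix 8 links the start of such a drug to uric acid.

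**Working it through.** **Figures in the plan.** Protocol 4.2 says hyperuricaemia-related events "also occurred in 7.8% (11/141 subjects) of the Japanese subjects treated with ETC-1002". Check: 11/141 = 7.8%, and Protocol 2.3 gives the parts, 6/141 = 4.3% and 5/141 = 3.5%. The design figure is 120 treated subjects with about 20 withdrawals: 100/(1 − 20/120) = 120. It reproduces and this point does not affect it.

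**Inputs not in the documents.** The share who start a urate-lowering drug and the fall it causes are both assumed. The 7.8% is the only proxy for the share. It is an adverse event rate, not a treatment rate, and it pools three doses.

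**Mean change at a late visit.** Understatement = share treated × fall caused.

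- 0.078 × 1 = 0.08 mg/dL
- 0.078 × 2 = 0.16 mg/dL
- 0.078 × 3 = 0.23 mg/dL
- Wider range: 0.02 × 1 = 0.02 up to 0.20 × 3 = 0.60 mg/dL, the latter taking both extremes together

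A share of 7.8% is about 9 of 120 subjects.

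**Simulation of timing and of the 9 mg/dL count.** 2,000 trials of 120 subjects and 13 visits. All inputs are assumed: baseline 5.5 mg/dL (SD 1.3), rise 0.8, within-subject SD 0.5, fall on treatment 2.0. At any visit where an untreated subject's value reaches the trigger, the drug is started with the stated probability. The triggers are modelling inputs; the documents give none.

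| Trigger (mg/dL) | Probability of acting | Share started | Week 52 mean change, no drug → observed | Ever ≥9, no drug → observed |
|---|---|---|---|---|
| 9 | 0.1 | 2.5% | 0.80 → 0.75 | 8.0% → 8.0% |
| 9 | 0.5 | 6.3% | 0.80 → 0.68 | 8.1% → 8.1% |
| 9 | 1.0 | 8.1% | 0.80 → 0.64 | 8.1% → 8.1% |
| 8 | 0.1 | 10.1% | 0.80 → 0.61 | 8.1% → 6.7% |
| 8 | 0.5 | 21.6% | 0.80 → 0.38 | 8.0% → 4.2% |
| 8 | 1.0 | 25.8% | 0.80 → 0.29 | 8.1% → 3.0% |

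The row nearest the proxy (8.1% started) loses 0.80 − 0.64 = 0.16 mg/dL, as the formula gives for a fall of 2. A trigger of 7 gives larger losses but has 26% to 54% of subjects starting the drug. The Week 4 mean is 0.80 with or without the drug in every run, because treatment can act only after a first on-treatment value has been seen.

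**Does stopping at drug start remove the bias?** Not fully. With rises that vary between subjects (SD 0.6) and treatment triggered at 8, a true Week 52 change of 0.80 became 0.30 to 0.41 with all data and 0.70 to 0.72 with pre-start values only. The remainder arises because the largest risers leave the summary.

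**The case against.** The case against has several sound parts.

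- **The 9 mg/dL count.** A reader might infer that this count, too, is understated at later visits. The documents do not support that. It counts a subject once over all post-dose treatment-period values, unscheduled ones included, and has no visit dimension. A subject who reached 9 before treatment stays counted. Only subjects treated before reaching 9 are missed, and the documents do not say whether sites would treat that early.
- **Treated subjects are not lost.** A reader might infer that they go unrecorded. Protocol 8.8.1 makes a laboratory value an adverse event when it is medically relevant, for example when it needs corrective treatment. Raised blood uric acid, hyperuricaemia and gout form a group of special interest in SAP Appendix 5, tabulated also by causality, statin response and eGFR. SAP 7.5 tabulates concomitant drugs by class and by preferred term, so each urate-lowering drug appears by name. Subject listings cover drugs and chemistry values.
- **The early rise stays visible.** Protocol 2.3 places it within the first month, so Week 4 in newly enrolled subjects should show it before most treatment could act.
- **The planned summary is legitimate.** Values under actual care are a fair description in an uncontrolled, descriptive trial.

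All of this narrows the point. What remains is that event and drug tables do not give the level of uric acid or its persistence. An intact Week 4 mean also does not correct the later ones; it makes a later fall look more like adaptation.

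**Conclusion.** The point holds for the by-visit uric acid means, the reference-range shift tables and the Last Visit summary. They are biased downward to the extent that urate-lowering drugs are started in response to a rise. At the phase 2 adverse event rate, used as a proxy for treatment, and an assumed fall of 1 to 3 mg/dL, the late mean change is understated by about 0.08 to 0.23 mg/dL. Actual use could be lower, since not every such event is treated, or higher, since exposure here runs to 52 weeks.

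Two stronger conclusions do not follow. It cannot be said that the uric acid effect of ETC-1002 will be materially hidden, because the documents give neither the rate of use nor its effect. Nor can it be said that the 9 mg/dL count is wrong in general. This is a worthwhile, inexpensive addition to the SAP, not a flaw that undermines the safety analysis.

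**What to change.** In SAP 9.3, for uric acid only, keep the planned all-data tables and add beside them:

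1. By-visit change and shift tables using values before the first start or dose increase of an antihyperuricemic after Day 1, with the number of subjects so treated by each visit. A footnote should say that this version also loses the largest risers, so it reduces the bias without removing it. The two versions are to be read together.
2. The number and percentage of subjects who reach 9 mg/dL or more, or who start or increase an antihyperuricemic after Day 1.

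Subjects already on such a drug at baseline are shown separately.

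The cost is a paragraph of SAP text, a predefined drug list and a few extra tables in Appendix 8. Protocol 6.5 already has indication, dose, and start and end dates recorded in the eCRF, so no new data are needed. The downside is fewer subjects at late visits in item 1, as well as the residual bias. No clinical rule changes.
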